6.2 Analysis Population

We will do a modified intention-to-treat analysis including all available data for participants who are included in the study population. Participants were excluded after randomization from the study population for the following reasons:

- Withdrawal of assent/consent before surgery
- Loss of candidacy for surgery

[Type here]

- Failure to obtain informed consent on the day of surgery for logistical reasons
- Presence of exclusion criteria on the day of surgery (N=5, occurring early in the study before the enrollment process was modified).

The number excluded after randomization for each reason will be indicated in the CONSORT diagram for the primary publication.

One (1) participant withdrew consent and (as allowed by state law) withdrew all data from the study. This participant will be noted by a footnote for the CONSORT diagram.

6.3 Covariates and Subgroups

The primary outcome measure (highest grade of PPC through POD 7) will be summarized for the following subgroups:

- gender (male; female)
- age (under 50; 50-80, over 80)
- BMI (under 18.5; 18.5-24.9; 25.0-29.9; 30-34.9)
- race (white / non-white)
- ethnicity (Hispanic / not Hispanic)
- duration of surgery (under 4 hours, 4-6 hours; > 6 hours)
- ASA physical status (I and II vs. III and IV)
- ARISCAT score (intermediate [26-44] vs high [45 or higher])
- Neuraxial intraoperative analgesia (Y/N)
- Neuromuscular blockade monitoring (quantitative vs qualitative/missing)
- Neuromuscular blockade reversal agent (Sugammadex vs Neostigmine)

6.4 Missing Data Imputation

As under 1% of participants withdrew EMR consent during the study, missing data imputation is not being done.

6.5 Interim Analyses

Two formal interim analyses were done using a Haybittle-Peto boundary ($P<0.001$) stopping for efficacy. The second interim analysis also included the possibility of stopping for futility. The adjusted significance level allowing for the interim monitoring is $P=0.0499023$ (two-sided; Z-score = 1.96080) for the primary endpoint.

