We will also compare biological measures of lung function and injury between the interventions: (1) lung mechanics and gas exchange; and (2) plasma biomarkers of lung injury at baseline, end of and 24±4h after surgery (see secondary outcomes).

Minimizing bias in outcome assessment: Study of each subject will involve at least 2 investigators per center: one to perform the randomization and implementation of the protocol in the operating room, and another, blinded to patient allocation, to assess for postoperative complications.

Analytic approach - secondary endpoints: The type of variable of the secondary outcome determines the approach used, as listed in Table 6 below:

Table 6. Approach for primary analysis according to the type of variable	
Type of Variable	Approach for Primary Analysis

Binary	For rare events ($\leq 5\%$): Fisher's Exact test For more common events ($>5\%$): Logistic regression (to allow for stratification by site)
Categorical (> 2 categories)	Cochran-Mantel-Haenszel test
Continuous	van Elteren test (an extension of the Wilcoxon Rank Sum test to allow for stratification by site)
Time to death	Cox Proportional Hazards Model
Repeated continuous outcomes (e.g. PROMIS® measures)	Mixed model Analysis of Variance

Additional analyses to fully explore the data will be specified in the SAP.

Interim analyses: We will perform two interim analyses after approximately 1/3 and 2/3 of participants have completed the 7-day follow up. Efficacy will be assessed using a Haybittle-Peto boundary of 0.001 at each analysis. We will be doing a futility analysis at the second interim analyses as well.

VII. RISKS AND DISCOMFORTS

The estimated risks and discomforts involved with participation in this study include:

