4.6 Sample Size

We estimated that 40% of participants in the control group would have pulmonary complications. If the bundle decreases the proportion of participants with complications by 35.29% (i.e, 25.88% would have complications in the intervention group compared to 40% in the control group), with no change in the distribution of the severity of complications, 750 participants (375 / treatment group), will provide 93% power to

detect the treatment effect as statistically significant (Cochran-Mantel-Haenszel test, row mean score test; $\alpha=0.05$, two-sided; based on simulations). The grant proposal contained a detailed discussion of the assumptions.

When the study was fully implemented the study team realized that approximately 6% of randomized participants would fail to be included in the study (revoking assent/consent on the day of surgery; no longer being a candidate for surgery; other reasons). The study team had not anticipated that this would occur. Therefore, we revised our plan to recruit approximately 795-800 participants to achieve 750 randomized participants having surgery with written consent.

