6.6 Multiplicity Considerations

There is one primary efficacy outcome, so multiplicity adjustment will not be made for it (i.e., $P < 0.05$ will be considered statistically significant, using the adjusted P -value specified in Section 6.5 for the primary endpoint). No formal adjustment for multiplicity will be made for secondary or exploratory measurements, but if the primary endpoint is not statistically significant, then these P -values will be considered another summary measure and not indicative of statistical significance between the treatment groups. Confidence limits are not adjusted for multiple comparisons and should not be used for hypothesis testing.

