8.1 Efficacy Outcomes

8.1.1. Primary Outcome: Highest Grade of PPC in the First 7 Days

This is analyzed using the Row-Mean-Score from a Cochran-Mantel-Haenszel test, stratified by site. As stated in Section 6.5 (Interim Analyses) a P-value of 0.0499023 (two-sided) will be used to determine statistical significance for a nominal alpha-level of 0.05.

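### The final significance level of 0.0499023 does not follow from two P<0.001 looks at about 1/3 and 2/3 unless an unstated binding futility rule was credited; without that credit the level is about 0.0495

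*SAP*

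**What the plan says.** The protocol, section VI, sets the monitoring plan: "We will perform two interim analyses after approximately 1/3 and 2/3 of participants have completed the 7-day follow up". The stopping rule follows: "Efficacy will be assessed using a Haybittle-Peto boundary of 0.001 at each analysis". It then adds: "We will be doing a futility analysis at the second interim analyses as well".

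SAP 6.5 reports that both looks took place with efficacy stopping at P<0.001, and says of futility: "The second interim analysis also included the possibility of stopping for futility". It then gives the final level: "The adjusted significance level allowing for the interim monitoring is $P=0.0499023$ (two-sided; Z-score = 1.96080) for the primary endpoint". SAP 8.1.1 applies it to the primary outcome: "a P-value of 0.0499023 (two-sided) will be used to determine statistical significance for a nominal alpha-level of 0.05". SAP 6.6 mentions 0.05 but defers to the adjusted value in 6.5.

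Neither document gives the information fractions at the looks as carried out, a futility cutoff, a statement that futility is binding, or the calculation behind 0.0499023.

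**The concern.** The figure is printed to seven decimal places as the level that accounts for the interim looks, so it should be reproducible from the number of looks, their timing and their boundary. All three are documented, and the standard calculation gives a different number.

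This is the decision threshold for the trial's only confirmatory test. Either the calculation used an assumption that is not written down, or the threshold corrects for too little of the interim testing. The sponsor can tell which; a reader cannot. If the primary P value fell just under 0.05, the claim of significance could rest on the answer.

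**Working it through.** **Inputs**

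- Overall alpha 0.05, two-sided (SAP 8.1.1).
- Two efficacy looks at P<0.001 (Protocol VI; SAP 6.5). Taken as two-sided, this is |Z| ≥ 3.2905.
- Looks at information fractions of about 1/3 and 2/3 (Protocol VI only).
- Printed final value: Z = 1.96080, P = 0.0499023 (SAP 6.5).
- Design power 93% with 750 participants (SAP 4.6).

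**Step 1. Are the printed P and Z consistent with each other?** 2 × (1 − Φ(1.96080)) = 0.049902. Yes, so this is not a rounding slip.

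**Step 2. Overall alpha at the printed value, with no futility credit.** Under no effect, Z1, Z2 and Z3 are jointly normal with corr(Zi, Zj) = √(ti/tj), where t = 1/3, 2/3, 1. Overall alpha is

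P(|Z1| ≥ 3.2905) + P(|Z1| < 3.2905, |Z2| ≥ 3.2905) + P(|Z1| < 3.2905, |Z2| < 3.2905, |Z3| ≥ c).

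Numerical integration gives:

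| Final c | Look 1 | Look 2 | Final | Total |
|---|---|---|---|---|
| 1.95996 (no adjustment) | 0.00100 | 0.00086 | 0.04865 | 0.05051 |
| 1.96080 (printed) | 0.00100 | 0.00086 | 0.04856 | 0.05041 |
| 1.96437 | 0.00100 | 0.00086 | 0.04814 | 0.05000 |

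The required value is c = 1.96437, P = 0.04949. The printed value removes 0.05051 − 0.05041 = 0.00010 of an inflation of 0.00051, about one fifth.

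**Step 3. Can "approximately" explain it?** Required final P by timing of the looks, with no futility credit:

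| Looks | Required P |
|---|---|
| 0.30 / 0.60 | 0.04939 |
| 1/3 / 2/3 | 0.04949 |
| 0.36 / 0.70 | 0.04955 |
| 0.40 / 0.80 | 0.04964 |
| 0.50 / 0.75 | 0.04976 |
| 0.60 / 0.80 | 0.04988 |
| 0.62 / 0.81 | 0.04990 |

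A first look at 1/3 with no second look at all already requires P = 0.04954. Even with the second look ignored, the first would have to fall at a fraction of at least 0.6186, which is 0.6186 × 750 ≈ 464 participants, against about 250 planned.

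**Step 4. Other readings of the boundary.** A one-sided 0.001 at each look requires P = 0.0488, further from the printed figure. To reach 1.96080 at 1/3 and 2/3, each look would have to use P<0.00026, which contradicts both documents.

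**Step 5. Futility credit.** If the trial must stop at the second look when |Z2| < f, those paths no longer contribute to the final term. At t = 2/3, f = 0.424 brings the total at c = 1.96080 to 0.0500. With drift set for 93% fixed-sample power (1.960 + 1.476 = 3.436), conditional power under the design effect at Z2 = 0.424 is

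Φ[(0.424√(2/3) + 3.436/3 − 1.960)/√(1/3)] ≈ 0.21,

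so such a cutoff is plausible. A one-sided stop at Z2 < 0.422 brings the benefit tail to 0.0250, but total two-sided alpha is then 0.0259.

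**Step 6. Consequences.** The chance that the final Z falls between 1.96080 and 1.96437 is 0.04% under no effect, 0.05% under the design effect, and 0.14% if the expected final Z is 1.96. Power is 93.01% at Z = 1.96080 and 92.96% at Z = 1.96437.

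**The case against.** The strongest reply is that this shows a reporting gap rather than an error. Futility at the second look is part of the documented design, so a calculation that ignores it omits a stated feature. The cutoff needed to make 1.96080 exact is close to a common one. With looks at 34% and 68% it is |Z2| < 0.457, where conditional power is 19.6% if design power is 93.0% and 20.2% if it is 93.5%. A binding rule at 20% conditional power would therefore reproduce the printed level within the rounding of the plan's own figures. Further, 1/3 and 2/3 is only the planned timing, the SAP takes precedence over the protocol, and any futility rule actually followed lowers the true error below 0.0504 (0.0503 for |Z2| < 0.2; 0.0502 for |Z2| < 0.3).

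Most of this stands as a possible explanation, and it is why the printed value should be kept if the inputs support it. It does not supply the missing rule. The protocol speaks of a futility analysis and the SAP of a possibility of stopping; neither gives a cutoff nor says that stopping was obligatory. The 20% rule and its binding status would be assumptions. On timing, the SAP states no alternative that could override the protocol, and only an implausibly late first look closes the gap.

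**Conclusion.** The concern holds, and it is minor. With looks at about 1/3 and 2/3, two-sided P<0.001 at each and no alpha credit for futility, the final level should be P=0.0495 (Z=1.9644). The printed 0.0499023 gives an overall alpha of about 0.0504. Among the explanations tried, a binding futility rule at the second look is the only one that fits the documented boundary and timing, and the documents do not state one.

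The result assumes that participant fractions approximate information fractions, that the test statistic is approximately normal with independent increments, and that the looks fell near their planned times. The practical effect is confined to a final P between about 0.0495 and 0.0499.

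**What to change.** Before the final analysis, recompute the threshold from the actual information fractions at the two looks, crediting futility only if a binding rule was specified in advance and followed. In SAP 6.5, state:

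- the number of participants and the information fraction at each look;
- the futility rule and whether it is binding;
- the derivation of the final level.

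If these inputs yield 0.0499023, keep it. If the looks were near 1/3 and 2/3 with no binding futility, replace it with P=0.0495 (Z=1.9644) in 6.5 and 8.1.1. Section 6.6 already defers to 6.5 and needs no separate figure.

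The cost is a few sentences and, if needed, one number in two places. Power falls by 93.01 − 92.96 = 0.05 percentage point.

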6.6 Multiplicity Considerations

There is one primary efficacy outcome, so multiplicity adjustment will not be made for it (i.e., $P < 0.05$ will be considered statistically significant, using the adjusted P -value specified in Section 6.5 for the primary endpoint). No formal adjustment for multiplicity will be made for secondary or exploratory measurements, but if the primary endpoint is not statistically significant, then these P -values will be considered another summary measure and not indicative of statistical significance between the treatment groups. Confidence limits are not adjusted for multiple comparisons and should not be used for hypothesis testing.

6.7 Calculation of Adjusted Variables

Some variables are calculated on an adjusted basis (e.g., per kg, per hour, etc.). If any element of the calculation (numerator or denominator) is missing, the value will be considered missing for the participant.

7 Summary of Study Data

7.1 Participant Disposition

Participant disposition will be summarized for a CONSORT diagram for the study.

7.2 Protocol Deviations

A list of protocol deviations is included in each report to the DSMB and will not be included in the final report for the study.

7.3 Summary of Baseline Characteristics

Baseline characteristics (specified in Section 5.1) will be summarized for the entire analysis population overall and separately by treatment group. Statistical tests **will not** be used for comparison of the treatment groups, consistent with CONSORT reporting principles.

7.4 Summary of Implementation Measures

Many implementation measures are collected only in the intervention group (e.g., number receiving pre-operative education). For implementation measures collected in both intervention and usual care groups, statistical tests will be done.

7.5 Summary of Intraoperative Characteristics

Intraoperative characteristics will be summarized for the entire analysis population overall and separately by treatment group. Statistical tests will be used for comparison of the treatment groups, as all intraoperative characteristics may be affected by the intervention.

8 Analysis of Outcomes

8.1 Efficacy Outcomes

8.1.1. Primary Outcome: Highest Grade of PPC in the First 7 Days

This is analyzed using the Row-Mean-Score from a Cochran-Mantel-Haenszel test, stratified by site. As stated in Section 6.5 (Interim Analyses) a P-value of 0.0499023 (two-sided) will be used to determine statistical significance for a nominal alpha-level of 0.05.

8.1.2 Other Efficacy Outcomes

Other efficacy outcomes are binary variables (presence/absence of a specific PPC or grade of PPC on a specific day) so will be summarized as counts (percents) and differences between groups assessed using a Cochran-Mantel-Haenszel test stratified by site.

8.2 Safety Outcomes

Safety outcomes will be analyzed as discussed in Section 6.1.4 (General Analysis Approach).

Appendix 1. ARISCAT Score Calculation

Table 1. ARISCAT risk score for PPCs⁴	
Variable	Score
Age (yr)	
≤ 50	0
51 – 80	3
> 80	16
Preoperative S _p O ₂ , %	
≥ 96	0
91 – 95	8
≤ 90	24
Respiratory infection in the last month	17
Preoperative anemia (≤ 10 g/dL)	11
Surgical incision	
Peripheral	0
Upper abdominal	15
Intrathoracic	24
Duration of surgery, h	
≤ 2	
> 2 to 3	0
> 3	16
	23

Appendix 2. Definition and List of PPCs from Protocol

Table 5. Operational Definitions of PPCs

Grade 1

Mild hypoxemia: $\text{SpO}_2 = 90\text{-}92\%$ on room air or the equivalent imputed $\text{PaO}_2/\text{FiO}_2$ ratio when oxygen therapy is provided

Mild respiratory findings: abnormal lung symptoms/signs (e.g., cough, dyspnea) and temperature $>37.5^\circ\text{C}$ without other documented cause; chest radiograph normal/unavailable

Grade 2

Cough: productive, no other cause

Bronchospasm: new or pre-existent wheezing resulting in therapy change

Hypoxemia: $\text{PaO}_2 < 60 \text{ mmHg}$ or $\text{SpO}_2 < 90\%$ on room air or the equivalent imputed $\text{PaO}_2/\text{FiO}_2$ ratio when oxygen therapy is provided

Respiratory Infection: use of antibiotic for suspected respiratory infection and at least one of the following: new or changed sputum, fever $>37.5^\circ\text{C}$, $\text{WBC} > 12,000/\text{mm}^3$

Atelectasis*: radiological confirmation + either temperature $>37.5^\circ\text{C}$ or abnormal lung symptoms/signs (e.g., cough, dyspnea)

Hypercarbia: transient, requiring treatment

Grade 3

Pleural effusion: resulting in thoracentesis

Pneumonia**, suspected: radiological evidence without bacteriological confirmation

Pneumonia**, proved: radiological evidence and documentation of pathological organism

Pneumothorax: resulting in intervention.

Ventilatory dependence: (non-invasive or invasive ventilation) $< 48\text{h}$

Grade 4

Ventilatory failure: postoperative non-invasive or invasive ventilation dependence $\geq 48\text{h}$

* **Atelectasis**: lung opacification with shift of the mediastinum, hilum or hemidiaphragm towards affected area and compensatory overinflation. ** **Pneumonia**: new and/or progressive pulmonary infiltrates on chest X-ray and two or more of: fever $\geq 38^\circ\text{C}$ or hypothermia ($<36^\circ\text{C}$); white blood cell count ($\text{WBC}/\text{mm}^3 > 12000$ or < 4000 ; purulent sputum and/or onset or worsening cough or dyspnea.

Appendix 3. Details of Targeted Adverse Events

- Rate of major extrapulmonary complications, defined based on existing diagnosis in the medical chart following usual accepted definitions⁶¹ unless otherwise specified:
 - Cardiovascular:
 - myocardial ischemia or infarction: Increase in serum cardiac biomarker values (preferably cardiac troponin) with at least one value above the 99th percentile upper reference limit and at least one of the following criteria⁶⁵:
 - Symptoms of myocardial ischemia;
 - New ischemic ECG changes;
 - Development of pathological Q waves;
 - Imaging evidence of new loss of viable myocardium or new regional wall motion abnormality in a pattern consistent with an ischemic etiology;
 - Identification of a coronary thrombus by angiography or autopsy.
 - cardiogenic pulmonary edema: Cardiogenic pulmonary edema is defined as evidence of fluid accumulation in the alveoli due to poor cardiac function.
 - arrhythmia: electrocardiograph (ECG) evidence of cardiac rhythm disturbance.
 - cardiac arrest: The International Liaison Committee on Resuscitation defines cardiac arrest as the cessation of cardiac mechanical activity, as confirmed by the absence of signs of circulation⁶⁸.
 - stroke: defined as an embolic, thrombotic or hemorrhagic cerebral event with persistent residual motor, sensory or cognitive dysfunction (e.g. hemiplegia, hemiparesis, aphasia, sensory deficit, impaired memory).
 - Gastrointestinal:
 - bleeding: Gastrointestinal bleed is defined as unambiguous clinical or endoscopic evidence of blood in the gastrointestinal tract. Upper gastrointestinal bleeding (or hemorrhage) is that originating proximal to the ligament of Treitz, in practice from the esophagus, stomach and duodenum. Lower gastrointestinal bleeding is that originating from the small bowel or colon.
 - anastomotic breakdown: Leak of luminal contents from a surgical connection between two hollow viscera. The luminal contents may emerge either through the wound or at the drain site, or they may collect near the anastomosis, causing fever, abscess, septicemia, metabolic disturbance and/or multiple organ failure. The escape of luminal contents from the site of the anastomosis into an adjacent localized area, detected by imaging, in the absence of clinical symptoms and signs should be recorded as a subclinical leak⁶⁹.
 - paralytic ileus: Failure to tolerate solid food or defecate for three or more days after surgery⁷⁰.

- Liver Disease:
Liver failure: serum bilirubin level $>34 \mu\text{mol/L}$ with elevation of the transaminase and lactic dehydrogenase levels above twice normal values.
- Acute renal failure: Stage 1 or higher Kidney Disease Improving Global Outcomes (KDIGO) guidelines⁷¹ (Table A1).

Table A1 Kidney Disease Improving Global Outcomes Guidelines (KDIGO)

Stage	Serum Creatinine	Urine Output
1	1.5–1.9 times baseline value within 7 days or $\geq 27 \text{ mmol/L} (\geq 0.3 \text{ mg/dL})$ increase within 48 h	$\leq 0.5 \text{ mL/kg/h}$ for 6–12 h
2	2.0–2.9 times baseline value within 7 days	$\leq 0.5 \text{ mL/kg/h}$ for 12 h
3	3.0 times baseline value within 7 days or Increase in serum creatinine to $\geq 354 \text{ mmol/L} (\geq 4.0 \text{ mg/dL})$ with an acute rise of $>44 \text{ mmol/L} (0.5 \text{ mg/dL})$ or Initiation of renal replacement therapy	$\leq 0.3 \text{ mL/kg/h}$ for 24 h or Anuria for 12 h

- Systemic inflammatory response syndrome (SIRS): Defined by the presence of two or more of the following⁶⁰
 - Temperature $>38^\circ\text{C}$ or $<36^\circ\text{C}$
 - Heart rate $>90/\text{min}$
 - Respiratory rate $>20/\text{min}$ or $\text{PaCO}_2 <32 \text{ mmHg} (4.3 \text{ kPa})$
 - White blood cell count $>12\,000/\text{mm}^3$ or $<4\,000/\text{mm}^3$
- Infections
 - Source uncertain: The CDC defines infection, source uncertain as one where there is strong clinical suspicion of infection but the source has not been confirmed because clinical information suggests more than one possible site, meeting two or more of the following criteria⁷² core temperature $<36^\circ\text{C}$ or $>38^\circ\text{C}$; white cell count $>12 \times 10^9/\text{L}$ or $<4 \times 10^9/\text{L}$; respiratory rate >20 breaths/minute or $\text{PaCO}_2 <4.7 \text{ kPa} (35 \text{ mmHg})$; pulse rate >90 beats/minute
 - Bacteremia (bloodstream infection): The CDC defines laboratory confirmed bloodstream infection as one which meets at least one of the following criteria⁷² which should not be related to infection at another site:
 - 1) Patient has a recognized pathogen cultured from one or more blood cultures and the organism cultured from blood is not related to an infection at another site.
 - 2) Patient has at least one of the following signs or symptoms: fever $> 38^\circ\text{C}$, chills or hypotension, and at least one of the following:

- a. Common skin contaminant cultured from two or more blood cultures drawn on separate occasions
- b. Common skin contaminant cultured from at least one blood culture from a patient with an intravascular line, and the physician institutes appropriate antimicrobial therapy
- c. Positive blood antigen test.
- **Sepsis:** defined following the Sepsis-3 criteria⁶⁰. Sepsis is a life-threatening organ dysfunction caused by a dysregulated host response to infection. Organ dysfunction can be identified as an acute change in total SOFA score ≥ 2 points consequent to the infection. The baseline SOFA score can be assumed to be zero in patients not known to have preexisting organ dysfunction. The SOFA score is included in the table below

Table 1. Sequential [Sepsis-Related] Organ Failure Assessment Score^a

System	Score				
	0	1	2	3	4
Respiration					
$\text{PaO}_2/\text{FiO}_2$, mm Hg (kPa)	≥ 400 (53.3)	<400 (53.3)	<300 (40)	<200 (26.7) with respiratory support	<100 (13.3) with respiratory support
Coagulation					
Platelets, $\times 10^3/\mu\text{L}$	≥ 150	<150	<100	<50	<20
Liver					
Bilirubin, mg/dL ($\mu\text{mol/L}$)	<1.2 (20)	1.2-1.9 (20-32)	2.0-5.9 (33-101)	6.0-11.9 (102-204)	>12.0 (204)
Cardiovascular	MAP ≥ 70 mm Hg	MAP <70 mm Hg	Dopamine <5 or dobutamine (any dose) ^b	Dopamine 5.1-15 or epinephrine ≤ 0.1 or norepinephrine ≤ 0.1 ^b	Dopamine >15 or epinephrine >0.1 or norepinephrine >0.1 ^b
Central nervous system					
Glasgow Coma Scale score ^c	15	13-14	10-12	6-9	<6
Renal					
Creatinine, mg/dL ($\mu\text{mol/L}$)	<1.2 (110)	1.2-1.9 (110-170)	2.0-3.4 (171-299)	3.5-4.9 (300-440)	>5.0 (440)
Urine output, mL/d				<500	<200
Abbreviations: FiO_2 , fraction of inspired oxygen; MAP, mean arterial pressure; PaO_2 , partial pressure of oxygen.					
^a Adapted from Vincent et al. ²⁷					
^b Catecholamine doses are given as $\mu\text{g/kg}/\text{min}$ for at least 1 hour.					
^c Glasgow Coma Scale scores range from 3-15; higher score indicates better neurological function.					

- **Surgical site infection:** defined as one which meets the following criteria⁷².
 - 1) Infection occurs within 30 days after surgery and
 - 2) Involves skin and subcutaneous tissue of the incision, or deep soft tissues (e.g. fascial and muscle layers) of the incision, or the infection appears to be related to the surgical procedure and involves any part of the body, excluding the skin incision, fascia or muscle layers opened or manipulated during the operative procedure.
 - 3) The patient has at least one of the following:
 - a. purulent drainage from the superficial/deep incision or from a drain that is placed through a stab wound into the organ/space
 - b. organisms isolated from an aseptically obtained culture of fluid or tissue from the superficial incision
 - c. at least one of the following symptoms or signs of infection:
 - i. pain or tenderness, localized swelling, redness or heat, and superficial incision is deliberately opened by surgeon and is culture positive or not

cultured. A culture negative finding does not meet this criterion.

- ii. a deep incision spontaneously dehisces or is deliberately opened by a surgeon and is culture-positive or not cultured when the patient has at least one of the following symptoms or signs: fever ($> 38^{\circ}\text{C}$), or localized pain or tenderness. A culture-negative finding does not meet this criterion.
- iii. an abscess or other evidence of infection involving the deep incision is found on direct examination, during surgery, or by histopathological or radiological examination.
- iv. an abscess or other evidence of infection involving the organ/space that is found on direct examination, during reoperation or by histopathological or radiological examination.

d. diagnosis of a surgical site infection by a surgeon or attending physician.

- Urinary tract infection: A simplified version of the CDC recommendations defines a urinary tract infection as follows: a positive urine culture of $\geq 10^5$ colony forming units per mL with no more than two species of micro-organisms, and with at least one of the following symptoms or signs: fever ($> 38^{\circ}\text{C}$), urgency, frequency, dysuria, suprapubic tenderness, costovertebral angle pain or tenderness with no other recognized cause⁷².

- Coagulation
 - Disseminated Intravascular Coagulation (DIC): defined following the 2001 definition by the International Society on Thrombosis and Hemostasis (ISTH): "DIC is an acquired syndrome characterized by the intravascular activation of coagulation without a specific localization and arising from different causes. It can originate from and cause damage to the microvasculature, which if sufficiently severe, can produce organ dysfunction"⁷⁴. It will be diagnosed following the modified algorithm currently used and described⁷⁵.

	
Acute DIC Algorithm Proposed by the International Society on Thrombosis and Haemostasis^a
 
Algorithm
 <hr/> 
1. Presence of an underlying disorder known to be associated with DIC? If yes: proceed. If no: do not use this algorithm2. Global coagulation results:
a. Platelet count ($>100,000/\mu\text{L} = 0$, $<100,000/\mu\text{L} = 1$, $<50,000/\mu\text{L} = 2$)b. Fibrin degradation products such as D-dimer (no increase = 0, moderate increase = 2, strong increase = 3)c. Prolonged prothrombin time (<3 seconds = 0, >3 seconds = 1, >6 seconds = 2)d. Fibrinogen level ($>1.0\text{ g/L} = 0$; $<1.0\text{ g/L} = 1$) <hr/> 
DIC, disseminated intravascular coagulation.
 
^aInterpretation of algorithm: A score of 5 or higher is compatible with acute DIC. The algorithm can be repeated on occasion if acute DIC remains a consideration and the laboratory values change. Modified from Taylor et al.⁶
	
--	---	--
